11.3.4 Stable disease (SD)

All of the following criteria must be met:

- a. Does not qualify for CR, PR, or progression.
- b. All measurable and non-measurable sites must be assessed using the same techniques as baseline.
- c. Stable clinically.

11.3.5 Unknown response status

Progressive disease has not been documented and one or more measurable or nonmeasurable lesions have not been assessed.

11.4 Methods for Evaluation of Disease

All measurements must be performed and recorded in metric notation using ruler, calipers, or digital measurement tools. All baseline measurement should be performed as close to initiation of treatment and never >4 weeks before the treatment.

The same method and technique of measurement should be used to characterize each identified and reported lesion at baseline and during follow-up. Imaging-based evaluation is preferred to evaluation by clinical examination unless the lesion(s) being followed cannot be imaged but are assessable by clinical exam.

11.5 Evaluation of Best Response

The best overall response is the best response recorded from the treatment start until disease progression (using as reference for progressive disease the smallest measurements recorded since the treatment started). If a response recorded at one scheduled MRI does not persist at the next regular scheduled MRI, the response will still be recorded based on the prior scan, but will be designated as a non-sustained response. If the response is sustained, i.e. still present on the subsequent MRI at least four weeks later, it will be recorded as a sustained response, lasting until the time of tumor progression. Participants without measurable disease may only achieve SD or PD as their best "response."

12. DATA REPORTING / REGULATORY REQUIREMENTS

Lists, guidelines, and instructions for reporting adverse events are listed in Section 7.

12.1 Data Reporting

Investigative sites are responsible for completing and submitting data and/or data forms according to the user requirements.

12.2 Data Collection

12.2.1 Data Collection Forms

The Miami Cancer Institute (MCI) Clinical Trial Office (CTO) will be responsible for all data management.

Case Report Forms will be generated by the CTO. Case Report Forms will be completed in a timely manner by the respective site. The trial will use a web-based Electronic Data Capture (EDC) system for all data collection. Case Report Form completion may be formally delegated to other study personnel listed in the delegation of authority (DOA) form and signed by the PI or co-investigator.

The following steps will ensure accurate, consistent, complete and reliable data:

- 1. The Investigator/Institution will conduct an initiation meeting at the study site prior to the start of the study. The study protocol, procedures and CRFs will be reviewed in detail and the study personnel will be trained to carry out the procedures defined in the protocol.
- 2. The Investigator will maintain a Study Site Binder for storing study related regulatory and study site documentation: study logs and forms.
- 3. All written study documentation entries must be made in blue or black ink. The investigator must review all entries for completeness and accuracy. When changes or corrections are made on any study documentation, the person making the change must draw a single line through the error, then initial and date the correction.
- 4. Periodic monitoring by the MCI CTO data management team will verify the accuracy of data entered on each CRF against the raw data from source documents at the site. Items needing correction/clarification will be identified and brought to the attention of the study site personnel and Principal Investigator, and corrections will be made as appropriate.
- 5. Once the Investigator/Institution performs a final review of the CRF, study database will be validated using appropriate validation processes.

12.2.2 Registration and Eligibility

The investigator will confirm patient eligibility. The investigator is responsible for enrolling only those patients who meet protocol eligibility criteria.

12.2.3 Data Safety and Monitoring Board (DSMB) Miami Cancer Institute DSMB will provide trial oversight per the Data Safety Monitoring Plan (DSMP).

12.3 Regulatory Requirements

12.3.1 Patient Consent Form

Informed consent must be obtained before protocol-specified procedures or interventions are carried out. The investigator will explain the nature of the study and will inform the subject that participation is voluntary and that they can withdraw at any time. A copy of the signed consent form will be given to every participant and the original will be maintained with the subject's records.

The consent form must be approved by the IRB. Consent forms are written to be understood by prospective subjects. The Informed Consent should be translated and certified into the local language of the respondent, as deemed necessary. Informed consent will be documented by the use of a written consent form approved by the IRB and signed and dated by the subject and by the person who conducted the informed consent discussion. The signature confirms the consent is based on information that has been understood. Each signed informed consent form must be kept on file by the investigator for possible inspection by Regulatory Authorities. The subject should receive a copy of the signed and dated written informed consent form and any other written information provided to the subjects, and should receive copies of any signed and dated consent form updates and any amendments to the written information provided to subjects.

12.3.2 Site Monitoring

To ensure compliance with current federal regulations and the ICH guidelines, data generated by this study must be available for inspection upon request by representatives of the FDA, national and local health authorities, and duly authorized representative of any entity providing support for this trial. Routine monitoring or audit activities for this study should be conducted by appropriately authorized personnel as warranted. The general scope of such visits would be to inspect study data (regulatory requirements), source documentation and CRF completion in accordance with current FDA Good Clinical Practices (GCP), the ICH guidelines and the respective local and national government regulations and guidelines.

12.3.3 Institutional Review Board Approval

This protocol, the informed consent document, relevant supporting information and all types of patient recruitment and advertisement information must be submitted to the local IRB for review and must be approved before the study is initiated. An amendment to remove a life-threatening situation can by implemented by the Investigator prior to obtaining IRB approval by the site. In such situations, the IRB must be notified immediately and the amendment forwarded to the IRB for their consideration.

The investigator is responsible for keeping the local IRB informed of the progress with study renewal at least once a year. The investigator must also keep the local IRB informed of any significant adverse events, per local institutional guidelines.

12.3.4 Records Retention

FDA regulations (21 CFR 312.62) require clinical investigators to retain all study-related documentation, including source document and CRFs for:

- Two years after the FDA approved the marketing application, or
- Two years after the FDA disapproves the application for the indication being studied, or
- Two years after the FDA is notified of the discontinuation of the trial, and that an application will not be submitted.

For all studies, including studies with FDA-IND exemption, the Investigator/ Institution will take measures to prevent accidental or premature destruction of study documents. For such studies conducted under IND exemption, records will be retained for a minimum of seven (7) years past official study termination. Sponsored trials should be contacted upon the study team becoming aware of the relocation of study documents or prior to destroying any study documents.

13. STATISTICAL CONSIDERATIONS

13.1 Study Design and Sample Size

We propose an open label, two parallel arm, two-stage, phase II trial to determine the efficacy, in terms of objective response rate (ORR), of combination therapy with tumor treating fields (TTFields) therapy, nivolumab with or without ipilimumab in adult patients with bevacizumabnaïve, recurrent glioblastoma. Best objective response rate (ORR) is defined as the proportion of evaluable patients who achieve complete (CR) or partial response (PR) according to modified immunotherapy iRANO criteria. Secondary objectives include safety, ORR by standard RANO criteria, overall survival (OS), progression-free survival (PFS), clinical benefit (defined as ORR plus stable disease >12 weeks), compliance rates of TTFields therapy at or above goal of 75%, and exploratory correlations between response or survival and compliance rates, serum and/or tumor tissue biomarkers. Primary analyses are performed for each arm, but secondarily assessed for the entire cohort as well.

The EF-11 study showed a response rate of 14% among patients with recurrent glioblastomas treated with TTFields alone compared to physician's choice medical therapy (Stupp et al, Eur J Cancer 2012). Thus, the null H0 is set at 14% and H1 (target ORR) set at 35% for each arm. Power is set at 85% with a 1-sided alpha of 0.05.

If no response is seen after 15 eligible patients are accrued in either arm, that arm will close for futility. Based on a MiniMax design, if >2 responses are seen on the first 15 patients in either arm, then 15 more patients will be accrued in the arm. If \geq 7 responses are seen among the 30 patients in either arm, this regimen deserves further investigation. Sample size will be 30 maximum per cohort/arm for a total of 30 to 60 subjects enrolled on study.

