5. TREATMENT PLAN

5.1 Study Design

This is an open-label Phase II trial with two parallel arms, two-stage design with appropriate stopping rules for poor efficacy. Arm A will enroll patients without prior history of any PD1/PDL1 checkpoint inhibitor, while Arm B will enroll patients with prior PD1/PDL1 checkpoint inhibitor. We expect to enroll at least 30 (15 in each Arm) and a maximum of 60 (30 in each Arm) evaluable subjects on this study. The study schema is depicted below.

NovoTTF200A (Optune) is a device to be worn continuously for a goal of \geq 75% of the time, ranging from 18 hours daily nonstop or 22 hours daily with 2-3 days off monthly. Patients will be encouraged to meet compliance goals via timely feedback and troubleshooting concerns. TTFields therapy begins once approved by insurance and an in-home initiation visit scheduled. The goal is to start within 1 month of starting immunotherapy infusions. Treatment is planned for ~24 months.

Infusions will start within 14 days of sreening/baseline visits. Nivolumab will be dosed every 2 weeks IV 240 mg as monotherapy and 3 mg/kg with ipilimumab. Nivolumab will not exceed 48 doses (24 months). Ipilimumab starts with the second infusion of nivolumab for Arm B (prior immunotherapy) or after progression on single agent nivolumab for Arm A (no prior immunotherapy). Ipilimumab infusions will be dosed as 1 mg/kg once every 6 weeks for a maximum of 4 doses (24 weeks).

Infusions will continue until maximum duration of ipilimumab and nivolumab therapy or when there is confirmed tumor progression, death, intolerable adverse effects or withdrawal. After the maximum of 24 months of therapy, clinical, radiographic and quality of life assessments are performed every 8 weeks until or when there is confirmed tumor progression, death, or withdrawal. One treatment cycle is defined as 6 weeks for the initial 24 months, thereafter every 8 weeks will define observation cycles.

Reported adverse events and potential risks are described in Section 7. Dose modifications are described in Section 6. No investigational or commercial agents or therapies other than those described below may be administered with the intent to treat the participant's malignancy.

5.2 **Pre-Treatment Criteria**

All patients must sign an informed consent prior to any study-specific procedure. For screening, patients will have the following tests done at the treating institution or in a local lab within 14 days of treatment initiation:

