13.5 Interim Monitoring

The study team will continuously monitor study accruals, toxicities and clinical outcome. Early stopping for futility will be considered after 15 patients have been enrolled and treated in each arm. Using a Minimax design, the chance of early stoppage under the null is calculated at 65%. The median time to response for nivolumab is 2 months. Once subject 15 is enrolled for each arm, we will wait a minimum of 8 (median time to response) and maximum of 12 weeks (2 MRI cycles) to assess response if an objective response by iRANO has not been noted in the already accrued patients.

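### The stage-1 futility rule gives no action for 1 or 2 responses in 15, and the stated 65% early-stopping chance matches stopping at 2 or fewer, not the written closing rule

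*Combined protocol and SAP*

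**What the plan says.** Section 13.1 states the design inputs: "Thus, the null H0 is set at 14% and H1 (target ORR) set at 35% for each arm", and "Power is set at 85% with a 1-sided alpha of 0.05". It names a Minimax design with 15 patients per arm at stage 1 and 30 in total. It then gives two stage-1 instructions:

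- Closing: "If no response is seen after 15 eligible patients are accrued in either arm, that arm will close for futility".
- Expanding: 15 more patients are added "if >2 responses are seen on the first 15 patients in either arm".

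Section 13.5 (Interim Monitoring) returns to the same look. It says "Early stopping for futility will be considered after 15 patients have been enrolled and treated in each arm", with no response count, and reports the operating characteristic: "Using a Minimax design, the chance of early stoppage under the null is calculated at 65" per cent. It also allows a wait of 8 to 12 weeks after the 15th patient, to be used "if an objective response by iRANO has not been noted in the already accrued patients".

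Section 5.1 says only "two-stage design with appropriate stopping rules for poor efficacy". Section 1.1 is equally general. Neither gives a boundary.

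**The concern.** The two instructions in 13.1 do not cover all outcomes. Zero responses closes the arm and three or more expands it; one and two are left out. Section 13.5 does not fill the gap. It speaks of stopping being considered, without a count, and its waiting clause is triggered by zero responses, as the closing sentence is.

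The stated 65% gives an independent check on which boundary was meant. If it disagrees with the written closing rule, the plan's only explicit futility rule conflicts with its own operating characteristic.

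The trial is open label and the primary endpoint is response. An arm with 1 or 2 responders would therefore be closed, held or continued at the team's discretion, with the responses already known. The oversight board would have no written boundary to apply. If such arms were continued, the reported early-stopping chance would no longer describe the trial. If they were simply not expanded, they would never be formally closed.

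**Working it through.** **Inputs.** From 13.1: p0 = 0.14, p1 = 0.35, one-sided alpha 0.05, power 85%, stage-1 n = 15, maximum n = 30 per arm. From 13.5: 65% early stopping under the null.

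**Step 1. Reproduce the 65%.** Let X be the number of responders among 15, X ~ Binomial(15, p), with P(X = x) = C(15, x) · p^x · (1 − p)^(15 − x).

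At p = 0.14:
- P(0) = 0.86^15 = 0.1041
- P(1) = 15 × 0.14 × 0.86^14 = 0.2542
- P(2) = 105 × 0.14² × 0.86^13 = 0.2897

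| Stop if responses in 15 are | P(stop), ORR 14% | P(stop), ORR 35% |
|---|---|---|
| 0 (the written closing rule) | 10.4% | 0.2% |
| 1 or fewer | 35.8% | 1.4% |
| 2 or fewer | 64.8% | 6.2% |
| 3 or fewer | 85.2% | 17.3% |

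Only stopping at 2 or fewer gives the stated 65%. Reading the expansion condition as a misprint for 2 or more does not help: it would mean stopping at 1 or fewer, which gives 35.8%.

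**Step 2. Confirm the intended design.** An exhaustive search over two-stage designs at p0 = 0.14, p1 = 0.35, one-sided alpha 0.05 and power 0.85 gives a smallest total of n = 30. Among designs of that size, the one with the lowest expected sample size under the null stops at 2 or fewer of 15 and rejects the null at 8 or more of 30. It has early stopping 0.648, alpha 0.0455 and power 0.852. The 15/30 sizes, the more-than-2 condition and the 65% all belong to this design. The zero-response closing sentence does not.

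**Step 3. Size of the gap.** P(1 or 2 of 15):
- ORR 14%: 0.2542 + 0.2897 = 0.5439, or 54.4%
- ORR 35%: 0.0617 − 0.0016 = 0.060, or 6.0%

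At least one of the two arms in the gap, taking the arms as independent:
- both at 14%: 1 − (1 − 0.5439)² = 79.2%
- both at 35%: 1 − (1 − 0.0602)² = 11.7%

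**Step 4. Consequence if gap arms were continued.** Expected N per arm under the null = 15 + 15 × (1 − P(stop)):
- stop at 2 or fewer: 15 + 15 × (1 − 0.6480) = 20.3
- stop at 0 only: 15 + 15 × (1 − 0.1041) = 28.4

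The difference is about 8 patients per inactive arm. It arises only if arms with 1 or 2 responses go on to stage 2. If they are not expanded, expected N stays at 20.3.

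**The case against.** The strongest reply is that the intended rule can be recovered. The second 15 patients are conditional on more than 2 responses, so nothing in 13.1 authorises expanding an arm with 1 or 2. Closing at zero is also correct under a 2-or-fewer rule, so the sentence can be called incomplete rather than contradictory. The sample sizes, the expansion condition and the 65% all point to the same boundary.

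The effect on error rates is also modest. With a final cut-off of 8 or more of 30, continuing the gap arms moves alpha from 0.0455 to 0.0496 and power from 0.852 to 0.876. With the 7 or more written in 13.1, alpha moves from 0.099 to 0.116.

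Much of this stands. The boundary can be inferred, the error-rate effect is small, and the main cost is enrolment, and only if gap arms are continued. The 79.2% also needs both arms to sit exactly at 14% and to be independent.

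It does not remove the defect. The plan's only explicit futility condition is zero responses, 13.5 repeats that framing in its waiting clause, and saying that stopping is to be considered makes even the inferred boundary discretionary. Someone applying 13.1 literally has no instruction to close an arm with 1 or 2 responses. Under 13.5 such an arm also gets no waiting period, although late responses could still take it to 3.

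**Conclusion.** The concern holds. As written, the stage-1 rule is undefined for 1 or 2 responses in 15, an outcome with probability 54.4% per arm at a 14% response rate and 6.0% at 35%. The stated 65% is correct for stopping at 2 or fewer (64.8%); the written closing rule gives 10.4%. The closing sentence in 13.1 and the waiting clause in 13.5 need correcting, and the 65% does not.

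The single-arm figures rest only on the plan's own p0, p1 and n = 15, with binomial responses. The two-arm figures also assume independent arms. The expected N of 28.4 applies only if gap arms are continued. This must be fixed, because it is the interim decision rule for the primary endpoint and it conflicts with the plan's own operating characteristic.

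**What to change.** In 13.1, replace the two stage-1 sentences with one exhaustive rule, keeping the plan's own term for the patients counted: *an arm with 2 or fewer responses among its first 15 patients closes for futility; an arm with 3 or more accrues a further 15.*

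In 13.5:
- apply the 8 to 12 week wait whenever fewer than 3 responses have been noted, instead of only when there are none;
- say that the arm closes under the 13.1 rule, instead of that stopping is considered;
- keep the 65%.

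Sample size, endpoint and population do not change. The one operational effect is that arms with 1 or 2 responses would now also wait before the decision. Stopping at 2 or fewer carries a 6.2% chance of closing an arm whose true response rate is 35%, against 0.2% for closing at zero. The Minimax design already counts this in its 85.2% power.

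That power, and its alpha of 0.0455, assume a final cut-off of 8 or more of 30, whereas 13.1 writes 7 or more. With stopping at 2 or fewer, the written cut-off gives alpha 0.099 and power 0.905. The final cut-off is a separate matter, but it should be reconciled in the same edit, because correcting stage 1 alone does not bring the design to its stated alpha of 0.05.

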13.4 Statistical Analyses

Baseline characteristics will be summarized using descriptive statistics: count, percentage, range, median, mean, and standard deviation as appropriate. Data include demographics (age, sex, race/ethnicity), performance status, laboratory parameters and prior therapy.

Treatment duration will be summarized by the number of immunotherapy cycles (6 weeks each). Frequency and reason for dose modifications and discontinuation of any therapy will be detailed.

We will report the objective response rate with corresponding two-side 90% confidence interval (CI) using the exact binomial method (Armitage et al, 2002). We will also report the objective response rate, the median and range for time to response, and duration of CR or PR. Time to progression will be summarized by the median and range for patients whose best response is SD as well as for all patients who develop progressive disease.

The Kaplan-Meier method will be used to estimate progression-free and overall survival. Point estimates for the proportion of progression-free and surviving patients will be given for selected times, specifically 6 and 12 months, along with corresponding 95% confidence intervals using the log-log transformed method and Greenwood's variance. To the extent possible with 30-60 study patients, we will investigate the relationship between tissue and serum biomarkers and overall response using logistic regression. Similarly, biomarker associations with progression free and overall survival will be explored using the log rank test and Cox regression.

Safety will be assessed by tabulating toxicities according to type, grade, duration, and attribution to study treatment in accordance with *NCI Common Terminology Criteria for Adverse Events* (CTCAE version 4.0). We will also report the distribution of worst grade toxicity in study patients.

TTFields compliance data is collect during monthly in-home visits by Novocure representative in order to assess NovoTTF200A (OptuneTM) function and address patient concerns. The compliance rates are an average (mean \pm stdev) over the 28-31 days of the month and provided in graphical and numerical form. Appendix D shows sample compliance reports with weighted average (mean \pm stdev) per month. These data are provided as part of standard of care and included in the patient medical record. The weighted average will be compared to ORR, OS and PFS using the appropriate logistic or Cox regression models.

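### The final success rule of 7 or more responses in 30 is one too low for the stated Minimax design: one-sided type I error per arm is about 0.10, not 0.05

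*Combined protocol and SAP*

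**What the plan says.** All the design inputs are in section 13.1, Study Design and Sample Size, and apply to each arm separately:

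- Hypotheses: "the null H0 is set at 14% and H1 (target ORR) set at 35% for each arm".
- Error rates: "Power is set at 85% with a 1-sided alpha of 0.05".
- Stage 1 continuation: "Based on a MiniMax design, if >2 responses are seen on the first 15 patients in either arm, then 15 more patients will be accrued".
- A second futility sentence: "If no response is seen after 15 eligible patients are accrued in either arm, that arm will close for futility".
- Maximum size: "Sample size will be 30 maximum per cohort/arm for a total of 30 to 60 subjects enrolled on study".
- Final decision, printed with a greater-than-or-equal sign in front of the number: "7 responses are seen among the 30 patients in either arm, this regimen deserves further investigation".

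Section 13.5, Interim Monitoring, adds: "Using a Minimax design, the chance of early stoppage under the null is calculated at 65" per cent. Section 13.4, Statistical Analyses, plans to report the response rate with a "two-side 90% confidence interval (CI) using the exact binomial method".

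**The concern.** A Simon two-stage design is usually tabulated by its rejection limits: r1 for stage 1 and r for the total. Both are the largest counts at which the regimen still fails, so success requires more than r. Section 13.1 treats the stage 1 limit this way (more than 2). Its final limit of 7, however, is given as a count that already succeeds. If 7 is the tabulated r, the success threshold is one response too low.

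This is the only go/no-go rule for the primary endpoint, and it is applied in both arms. The 14% null is the response rate the protocol attributes to TTFields alone. A false positive therefore means taking forward a combination that responds no better than the device by itself.

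**Working it through.** **Inputs.** From section 13.1: p0 = 0.14, p1 = 0.35, one-sided alpha 0.05, power 0.85, n1 = 15, continue if more than 2 respond (r1 = 2), N = 30, success at 7 or more. From section 13.5: 65% early stopping under the null.

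**Formulas.** Let X1 and X2 be independent binomial counts, each from 15 patients with response rate p, and let s be the success threshold.

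- Early stopping: P(X1 ≤ r1).
- Success: Σ over x1 > r1 of P(X1 = x1) × P(X2 ≥ s − x1).

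Success at p = 0.14 is the type I error; at p = 0.35 it is the power.

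**Step 1: reproduce the plan's design.** An exhaustive search for p0 = 0.14, p1 = 0.35, alpha ≤ 0.05 and power ≥ 0.85, taking the smallest N and then the smallest expected N under the null, returns n1 = 15, r1 = 2, N = 30, r = 7. Early stopping is P(X1 ≤ 2) = 0.1041 + 0.2542 + 0.2897 = 0.648, which is the plan's 65%. Stage sizes, continuation rule and early stopping all match. In this solution success means more than 7, so s = 8.

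**Step 2: type I error with s = 8, p = 0.14.**

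| x1 | P(X1 = x1) | P(X2 ≥ 8 − x1) | Product |
|---|---|---|---|
| 3 | 0.2044 | 0.0479 | 0.0098 |
| 4 | 0.0998 | 0.1477 | 0.0147 |
| 5 | 0.0357 | 0.3520 | 0.0126 |
| 6 | 0.0097 | 0.6417 | 0.0062 |
| 7 | 0.0020 | 0.8959 | 0.0018 |
| ≥ 8 | 0.0004 | 1 | 0.0004 |
| Sum | | | **0.0455** |

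The same sum at p = 0.35 gives power 0.8522. Both stated error rates are met.

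**Step 3: type I error with s = 7 as printed, p = 0.14.**

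| x1 | P(X1 = x1) | P(X2 ≥ 7 − x1) | Product |
|---|---|---|---|
| 3 | 0.2044 | 0.1477 | 0.0302 |
| 4 | 0.0998 | 0.3520 | 0.0351 |
| 5 | 0.0357 | 0.6417 | 0.0229 |
| 6 | 0.0097 | 0.8959 | 0.0087 |
| ≥ 7 | 0.0024 | 1 | 0.0024 |
| Sum | | | **0.0993** |

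Power at p = 0.35 is 0.9047. Counting exactly 7 of 30 as a success adds 0.0993 − 0.0455 = 0.0538 to the type I error.

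**Step 4: does another reading of the futility rule rescue 7 or more?**

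| Stage 1 rule | Alpha, ≥ 7 | Power, ≥ 7 | Alpha, ≥ 8 | Power, ≥ 8 |
|---|---|---|---|---|
| Stop at 0 of 15 | 0.1163 | 0.941 | 0.0496 | 0.876 |
| Stop at ≤ 1 | 0.1132 | 0.936 | 0.0490 | 0.873 |
| Stop at ≤ 2 | 0.0993 | 0.905 | 0.0455 | 0.852 |
| Stop at ≤ 3 | 0.0692 | 0.813 | 0.0357 | 0.780 |
| No stopping | 0.1165 | 0.941 | 0.0497 | 0.876 |

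Alpha exceeds 0.05 in every row with 7 or more. With 8 or more, both stated limits are met in every row except stopping at 3 or fewer, a rule the plan does not use.

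**Step 5: was alpha 0.10 intended?** The same search at alpha 0.10 and power 0.85 gives a Minimax maximum of 23 patients; at alpha 0.10 and power 0.90 it gives 28. The plan's 30 corresponds to alpha 0.05 with power 0.85.

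**Step 6: the planned interval.** The exact two-sided 90% interval is 11.5% to 39.4% at 7/30, which includes 14%. At 8/30 it is 14.02% to 43.0%, which just excludes it.

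**Step 7: both arms.** If both arms are truly at 14% and independent, the chance of at least one false positive is 1 − (1 − 0.0993)² = 0.189 with 7 or more, and 1 − (1 − 0.0455)² = 0.089 with 8 or more.

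**The case against.** Several points can fairly be made for the plan as written.

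- **Not every figure fails.** The 65% depends only on the stage 1 rule, and 85% power is exceeded at 7 or more. This is true: only alpha breaks under the printed threshold. But alpha is the stated constraint, and the full set of figures together points to the design that needs 8.
- **The attained values are conditional.** Section 13.1 has two futility sentences and leaves 1 or 2 responses in 15 unresolved. The 0.0455 and 0.852 hold only if an arm stops at 2 or fewer. This stands as a condition. The stated 65% supports that rule, since stopping only at 0 of 15 gives 10.4%. Under either rule, 8 or more meets the stated limits and 7 or more does not.
- **The interval is for reporting, not decision.** It also ignores the two-stage design, and the margin at 8/30 is thin. Both are correct, so it is supporting evidence only.
- **No control across arms is claimed.** Also correct; the two-arm figures show consequence, not a departure from the plan.
- **It is a phase II screen.** A lower bar costs more false leads but misses fewer active regimens. That could be a legitimate choice, but the plan would then have to state an alpha of about 0.10.
- **The sign could be a text-extraction error.** This is unlikely, because a plain greater-than sign survives before the 2 in the same paragraph. Checking the original PDF would settle it.

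**Conclusion.** The concern holds. With success at 7 or more of 30, the one-sided type I error per arm is 0.099 if an arm stops at 2 or fewer of 15, and 0.116 if it stops only at 0 of 15, against a stated 0.05. The threshold that fits the plan's own inputs is 8 or more.

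This rests on exact binomial calculation, the 14% and 35% rates as given, full accrual of 15 and 30 evaluable patients, and adherence to the stage 1 rule. That the design's r was copied as a success count is an inference about how the slip arose; the size of the error does not depend on it. It must be fixed, because the primary decision rule does not deliver its stated error rate.

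**What to change.** In section 13.1, change the final rule so that an arm succeeds with 8 or more (more than 7) responses among 30 patients. State the attained one-sided alpha of 0.046 and power of 0.852, with the condition that an arm stops at 2 or fewer responses in 15. Reconcile the two futility sentences with that condition; if stopping only at 0 of 15 is meant, the attained values are 0.0496 and 0.876, and the 65% in section 13.5 must change to 10.4%.

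If 7 or more is a deliberate choice, keep it and restate the one-sided alpha as about 0.10 and the power as about 0.90, assuming stopping at 2 or fewer.

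The threshold correction changes one number. It needs no extra patients and keeps the stated 85% power; relative to the printed rule, power falls from 0.905 to 0.852.
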